Application of one-handed lithotripsy in percutaneous nephrolithotomy

Clinical study protocol

1. Title: Application of one-handed lithotripsy in percutaneous nephrolithotomy.
2. Trail registration: Clinical Trials Registry (<https://www.clinicaltrials.gov>) 。
3. Version number and date: Version number: V1.0 Version Date: November 19, 2022。
4. Funding: New technology of the First Affiliated Hospital of the University of South China
5. Investigator and responsibilities: [name], deputy chief physician (study leader) : trial design, surgical implementation, protocol management, and process guidance; Research group postgraduate: data collection and analysis, article writing and publication.
6. Research background and principle: Percutaneous nephrolithotomy(PCNL)is the treatment of choice for staghorn stone,complex renal caculi,large volume calcilo (especially ≥ 2 cm in diameter) .This procedure is the highest level of urology surgery and is characterized by high difficulty and high risk.Traditional PCNL usually adopt the left hand holding nephroscope to adjust depth and direction of the lens and the right hand to control the fiber for lithotripsy.It requires the operator to undergo long-term practical training to achieve tacit cooperation between the hands.There are analysis of the learning curve for percutaneous nephrolithotomy suggests that operators take at least 20 cases of PCNL to learn basic surgical skills, and at least 60 cases to initially master surgical competence.So, we propose a new surgical method - one-handed lithotripsy technique.The core of this technology is to use the same hand to hold the nephroscope and control the laser fiber,thereby avoiding the running-in problem of the two hands controlling the nephroscope and the laser fiber respectively, and the operator can continuously adjust the fiber and nephroscope to continuously crush the litholysis during the surgery, which significantly shortens the learning curve, operation time and difficulty of PCNL.Therefore, we believe that the promotion and

popularization of percutaneous nephroscopic with one-handed lithotripsy is of great clinical practical significance.

7.Objective: : The purpose of this study is to explore the safety and clinical efficacy of this new surgical method in the treatment of upper urinary calculi by combining the application of one-handed lithotripsy in the PCNL.

8.Experimental design: : A two-arm parallel trial design was carried out.The participants who underwent PCNL with one-handed lithotripsy were selected as the experimental group, and the participants who underwent traditional PCNL were selected as the control group.Prospective exploration studies were conducted on a 1:1 basis.

9.Site: This was a single-center study conducted at the First Affiliated Hospital of the University of South China

10.. Inclusion and exclusion criteria:1.Participants who met the the applications of PCNL surgery in the 2019 Chinese Guidelines for the Diagnosis and Treatment of Urological Diseases; 2. Participants who agree to undergo PCNL with one-handed lithotripsy.Exclusion Criteria: 1).Obvious surgical contraindications, such as severe heart and lung insufficiency, abnormal coagulatory function.2) If the following variations occurred during the operation: a finding that pyonephrosis demanded the treatment of nephrostomy,channel bleeding that was required to maintain a nephrostomy tube,or incomplete postoperative clinical data will be recorded by the study recruitment flow chart, but not included in the final data analysis

11.Intervention measures:

a. According to the randomization, the same associate chief urologist performed PCNL with one-handed lithotripsy or traditional PCNL;

b.During the perioperative period, participants were given comprehensive blood biochemical examination and imaging evaluation, and antibiotics (second-generation cephalosporins or penicillins) were prophylactic.Participants with hypertension, diabetes and other comorbidities were given relevant drugs to control the tolerable level of surgery.

c. Implementation process of PCNL with one-handed lithotripsy:

a).After general anesthesia, the patient was placed in lithotomy position, routinely

[figure not shown]
disinfected and covered with towels. Transurethral cystoscopy/ureteroscopy was performed to observe the ureteral opening on the affected side, and the ureteral catheter was retrograde inserted at a depth of 15 to 25cm. Exit the ureteroscope and fix the ureteral catheter on the urinary catheter. Then, the patient was moved to prone position, disinfected again and covered with towel, suffer renal biopsy under ultrasound guided look straight into the target under the calyces, syringe after water injection and suction is smooth, the guide wire guided by micro fascia dilator (Fr16 or Fr18) continuous build percutaneous renal channel expansion. Holmium laser was used for lithotripsy

b). According to different lithotripsy methods, the operation was randomly divided into group 1 (one-handed lithotripsy group): using one hand to control the nephroscope and laser fiber at the same time, the other hand to adjust the depth and angle of the sheath at same time. Group 2 (traditional lithotripsy group) : lithotripsy was carried out by holding the nephroscope with one hand and controlling the laser fiber with the other one. It was often necessary to stop the lithotripsy to adjust the depth and angle of the sheath.

c). After the broken stones were removed, the ureteropelvic opening was located, the guide wire was placed anteriorly, and the ureteral stent was placed under the guidance of the guide wire. After no residual calculi were detected under the nephroscope, the endoscope was removed and the nephrostomy tube was indwelled and fixed. The incision skin is then sutured.

12. Outcome measures : The primary clinical end point are operative time 、 stone clearance rate 、 number of tracts 、 rate of second operation 、 rate of auxiliary procedure 、 intraoperative renal pelvis mucosal injury rate 、 the incidence of postoperative complications (including postoperative fever, bleeding, pain, and changes in renal function; Ureterostone street was formed after operation. Air-fluid chest after operation) ; The secondary clinical end points were operation time, hospital stay, hospital cost.

13. Recruitment flow chart:

14. Sample size: Combined with the number of outpatient calculi patients and the number of PCNL surgeries in our department of Urology each year, we planned to initially include 100 patients with renal and/or upper ureteral calculi who underwent traditional PCNL surgery in our hospital from November 2022 to November 2023, and randomly assigned at 1:1.

15. Participants: Patients with upper urinary stones attending the Urology Clinic of the First Affiliated Hospital of the University of South China were recruited

16. Allocation sequence generation, allocation hiding, implementation methods: Using the coin toss method, patients with the flip side of the coin were divided into PCNL surgery group using one-handed lithotripsy technique (group 1), and patients with the reverse side of the coin were assigned to the traditional PCNL procedure group (group 2). This process takes place in the operating room

17. Blinding: : In a single-blind approach, patients are told to participate in a clinical trial but are not informed about the specific intervention, while the person administering the intervention is clearly informed.

18. Data collection: The measured data of all the required: : 1. The demographic data, stone characteristics and preoperative baseline data, including the proportion of gender, age, body mass index (BMI) and basic diseases distribution, location, stones, stone maximum cross-sectional area, the longest diameter antler shape proportion and

pelvic effusion width, partial side and puncture operation, etc.2.Data of the main end points included:operative time、 stone clearance rate、 number of tracts、 rate of second operation、 rate of auxiliary procedure、 intraoperative renal pelvis mucosal injury rate、 the incidence of postoperative complications (including postoperative fever, bleeding, pain, and changes in renal function; Ureterostone street was formed after operation. Air-fluid chest after operation) ; Secondary end points included:postoperative renal function changes, operative blood loss, postoperative bleeding rate, postoperative patient pain score, postoperative inflammation changes。

19. Statistical analysis plan: SPSS26.0 statistical software was used for analysis.

Measurement data were expressed as mean \pm standard deviation ($X \pm S$) and t-test was used. Enumeration data were expressed as frequency and percentage by X^2 or Fisher exact test. Rank sum test was used for rank data. $P < 0.05$ was considered statistically significant.

20.Ethical approval: This trial was a human life science and medical study and was approved by the Medical Ethics Committee of the First Affiliated Hospital of the University of South China. (No: 2022111120001)

21.Informed consent: All participants enrolled in the study signed a surgical consent and a clinical trial informed consent to collect and use the medical behavior information and biological samples for the study

22.Confidentiality measures: The identifiable information of the subjects is replaced by irrelevant character sequences to ensure that the relevant personal information of the subjects will not be disclosed in any form.

23.Declaration of Interest: There is no conflict of interest between the investigator and the organization.

24.. Data Acquisition: : When proper editing or review requirements are met, the study data may be obtained from the study manager after the study is completed.

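### Do the eligibility, blinding and sample-size sections contradict each other on who is enrolled and what patients are told?

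*Protocol*

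**What the plan says.** Three statements bear on who enters the trial and what they know.

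- Section 10, inclusion criterion 2: "Participants who agree to undergo PCNL with one-handed lithotripsy". It mentions neither the control technique nor random assignment.
- Section 17 (Blinding), under a single-blind heading: "patients are told to participate in a clinical trial but are not informed about the specific intervention". The operator, by contrast, is informed.
- Section 14 (Sample size): "we planned to initially include 100 patients with renal and/or upper ureteral calculi who underwent traditional PCNL surgery in our hospital". The same sentence ends with the patients being "randomly assigned at 1:1".

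Other sections describe the conduct of the trial. Section 11a states: "According to the randomization, the same associate chief urologist performed PCNL with one-handed lithotripsy or traditional PCNL". Section 15 recruits patients with upper urinary stones from the urology clinic. Section 16 allocates by coin toss between the two techniques and places the toss in the operating room. Section 21 says that every participant "signed a surgical consent and a clinical trial informed consent".

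**The concern.** Taken literally, each statement implies something different. If every participant must agree to the one-handed technique, every participant has been told of it, including those who then receive the control. If patients are told nothing about the interventions, they cannot give that agreement. If the whole sample had already undergone traditional PCNL, there would be nothing left to randomise.

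Two things could be at stake. One is the enrolled population, which might be read as people who accepted the new method rather than people willing to have either. The other is patient blinding, the only blinding the protocol claims. Blinding matters most for pain, which is part of the complications endpoint among the primary outcomes (section 12) and also a secondary pain score (section 18). If control patients knew that they had missed the technique they agreed to, a pain difference would be hard to interpret.

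**Working it through.** The protocol gives no effect size, standard deviation, event rate or power, and section 14 sets the 100 patients from clinic and surgical volume. There is therefore no calculation to reproduce. The check is a comparison of passages, one count and one line of algebra.

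**1. Section 14 against the two-arm design.** With 100 patients at 1:1, the expected number per arm is 100 × 1/2 = 50. Having had traditional PCNL can thus describe about 50 of the 100, not all of them. The phrase is wrong as written. But the same sentence randomises these patients, and sections 8, 11 and 16 all have two arms. Section 15 recruits people attending the clinic with stones. The protocol also uses the past tense for planned events in other places, for instance when it describes the design and the recruitment. The workable sense is candidates for PCNL.

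**2. Inclusion 2 against section 17.** There are two readings of what section 17 withholds.

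- The assigned arm is withheld. Patients may know that both techniques exist, must be willing to have the new one, and do not learn which was used. Inclusion 2 and section 17 then agree. The contrast with the informed operator, under a single-blind heading, favours this reading.
- The existence of two techniques is withheld. Inclusion 2 then could not be met. This reading is possible but strained, because it would defeat the protocol's own eligibility rule.

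**3. Effect on the pain comparison.** Let T₁ and T₂ be mean pain in the one-handed and traditional arms without any expectation effect. Let e₁ and e₂ be the shift that expectation adds in each arm, taken as additive. Then

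observed difference = (T₁ + e₁) − (T₂ + e₂) = (T₁ − T₂) + (e₁ − e₂).

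Agreement under Inclusion 2 is an entry condition, so it comes before the coin toss and is the same for everyone. Hence e₁ = e₂, the last term is zero, and the observed difference equals T₁ − T₂. This holds under either reading in step 2, because what patients are told before allocation does not depend on the arm. Bias would need control patients to learn their arm afterwards. Section 17 rules that out, and surgery is under general anaesthesia (section 11).

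**4. Reach.** Section 12 lists seven primary endpoints. Pain is one component of one of them. The other six (operative time, stone clearance, number of tracts, second operation, auxiliary procedure and mucosal injury) are not patient-reported.

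**The case for a change.** The best argument for acting is that eligibility is for the protocol to settle, not something to leave to a later analysis plan, and that the reconciling reading relies on words neither section contains. Inclusion 2 does not say willing to receive either technique, and section 17 does not say that only the arm is withheld. Section 8 offers limited help, since it too describes the groups by the operation patients had. The repair would be cheap: a few words in three sections.

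Much of this stands as a comment on drafting. Section 14 is wrong as written, and Inclusion 2 is one-sided. What does not stand is the step from wording to harm. No route is shown by which control patients would learn their arm. That about 50 control patients do not receive the experimental technique is true of any two-arm trial with this allocation, and it measures no error. A mismatch between consent and treatment is not shown either: section 21 records a trial consent for all participants, and the text of that form is not available for review. A further rule to conceal the arm until the last pain assessment would add little, since section 17 already withholds it and sets no point at which it is disclosed.

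**Conclusion.** The wording is inconsistent, most plainly in section 14, but no change to the plan follows. A team following sections 11, 15, 16 and 17 would enrol the same patients, randomise them in the same way and obtain the same results with or without the rewording. The effect on sample size, endpoints and tests is nil, and no between-arm bias in pain is shown.

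This rests on three assumptions: that agreement is obtained before the coin toss, as an eligibility criterion must be; that patients are not told their arm afterwards, as section 17 states; and that the trial consent describes random assignment, which cannot be verified here. If the protocol is revised for other reasons, the three phrases could be tidied then, but the point does not justify an amendment of its own.

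### Section 10, Exclusion 2 removes patients from the final analysis for channel bleeding that can follow allocation and for incomplete postoperative data that must follow it

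*Protocol*

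**What the plan says.** Section 10 lists Exclusion 2 among the exclusion criteria, but its lead-in is "If the following variations occurred during the operation". It names three triggers: pyonephrosis that needs nephrostomy, "channel bleeding that was required to maintain a nephrostomy tube", and missing postoperative data. The consequence is stated outright: such cases, including those with "incomplete postoperative clinical data will be recorded by the study recruitment flow chart, but not included in the final data analysis".

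The sections that bear on this are:

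- **Aim and design.** Section 7 sets out to "explore the safety and clinical efficacy of this new surgical method". Sections 8, 14 and 16 make this a two-arm comparison of 100 patients randomised 1:1.
- **Moment of allocation.** Section 16 places the coin toss in the operating room. Section 11.a says "According to the randomization, the same associate chief urologist performed PCNL with one-handed lithotripsy or traditional PCNL", which can be read as a toss before surgery. Section 11.c.b says "According to different lithotripsy methods, the operation was randomly divided into group 1", and it comes after the description of building the tract.
- **Blinding.** Under section 17 the operator knows the arm.
- **Endpoints.** Postoperative bleeding is part of a primary endpoint (section 12). Operative blood loss is secondary (section 18). Operative time, number of tracts and "intraoperative renal pelvis mucosal injury rate" are primary (section 12).
- **Analysis.** Section 19 names the tests but no analysis set, so it does not undo the rule in section 10.

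**The concern.** Randomisation makes the two groups comparable as they stand at the toss. A rule that removes patients for something that happens later, and that the technique or its operator may influence, no longer compares those groups.

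Here one trigger lies close to the outcomes. Patients with notable channel bleeding are likely to have high operative blood loss, and some may go on to postoperative bleeding. The trigger is not the same outcome as postoperative bleeding, but the two are plausibly related. Any arm difference that runs through the trigger is removed from the endpoint results. If the rule is applied unequally by arm, a difference that does not exist can appear. The operator is unblinded, and no passage says who judges the bleeding trigger.

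The missing-data trigger does separate damage. It deletes the whole patient, including endpoints already known when surgery ends.

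The bleeding trigger is also loosely defined. In section 11.c.c the routine procedure finishes when "the endoscope was removed and the nephrostomy tube was indwelled and fixed", so a need to maintain a tube does not clearly separate excluded from included patients.

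**Working it through.** **1. Timing of each trigger against the toss**

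| Trigger (section 10) | Relation to the operating-room toss (section 16) |
|---|---|
| Incomplete postoperative data | Always after |
| Channel bleeding that starts during lithotripsy | Always after, because the arms differ only in lithotripsy technique (11.c.b) |
| Channel bleeding during access | Before or after; the moment of the toss is not fixed |
| Pyonephrosis | Before or after, for the same reason |

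If the toss follows access, excluding patients for the last two is legitimate. The first two rows do not depend on that.

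**2. No plan figure to reproduce.** The 100 patients in section 14 come from clinic and surgery volume. No effect size, SD, event rate, power or dropout is given. Everything below uses assumed inputs to show scale, with 50 patients per arm and two-sided 0.05.

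**3. (a) Trigger and postoperative bleeding kept separate; all trigger cases arise after allocation and are dropped.** Let t be the trigger rate, b1 the postoperative bleeding rate with the trigger and b0 the rate without it. The rate in all randomised patients is t·b1 + (1−t)·b0, and the analysed rate is b0. Assume t = 10% v 4% and b0 = 4%.

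| b1 | All randomised | Difference | Analysed |
|---|---|---|---|
| 20% | 5.60% v 4.64% | 1.0 points | 4% v 4% |
| 40% | 7.60% v 5.44% | 2.2 points | 4% v 4% |
| 60% | 9.60% v 6.24% | 3.4 points | 4% v 4% |

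For operative blood loss, if trigger patients lose d SD more, the difference removed is (0.10 − 0.04)·d. This is 0.06 SD for d = 1 and 0.12 SD for d = 2.

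**4. (b) Excluded patients would have counted as bleeders; the same fraction f is dropped in both arms.** The analysed rate is p(1−f)/(1−pf). Take p = 15% v 5% and f = 0.50:

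- 0.075/0.925 = 8.11% and 0.025/0.975 = 2.56%, so the difference falls from 10 to 5.5 points.
- The odds ratio stays at 3.35; the risk ratio moves from 3.00 to 3.16.
- Exact Fisher power falls from 24.4% (50 v 50) to 12.3% (46 v 49, from 50 × 0.925 and 50 × 0.975).

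**5. (c) Unequal dropping with no true difference.** Take p = 10% in both arms and f = 75% v 25%:

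- 0.025/0.925 = 2.70% and 0.075/0.975 = 7.69%, a false difference of 5.0 points.
- Fisher's test rejects in 6.2% of trials (46 v 49), against 1.8% with all patients kept.
- With the separate outcomes of (a) and t = 10% in both arms, the analysed rate is [b0(1−t) + b1·t(1−f)]/(1−tf). The false difference is then 0.8, 1.8 or 2.8 points for b1 = 20%, 40% or 60%.

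**6. (d) Operative time.** Suppose operative time has correlation r with bleeding severity and the worst fraction q is removed. The mean of those left shifts by −r·φ(z)/(1−q), where z is the normal point with upper tail q. With q = 0.075 v 0.025, as in (b), the arms shift relative to each other by 0.028 SD (r = 0.3) or 0.047 SD (r = 0.5), which is small.

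**7. Loss from deleting the whole patient.** Two-sided t-test power for a 0.5 SD difference is 69.7% with 50 per arm, 65.0% with 45 (10% incomplete) and 59.8% with 40 (20% incomplete). For operative time this loss is avoidable, because the value is known when surgery ends.

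**The case against.** The strongest reply concerns the bleeding trigger. Section 11.c.a builds the tract identically in both arms, random division is first described at the lithotripsy step, and section 10 pairs channel bleeding with pyonephrosis. A natural reading is that both are access-stage findings made before the compared technique is used; if the toss comes after access, no bias follows from them. The recruitment flow chart of section 13, which is not visible in the available text, might settle this. That reply stands for access-stage events. It does not reach bleeding during lithotripsy, which the wording does not rule out, and it leaves incomplete data untouched.

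A second reply is that the flow chart records the exclusions. If it does so by arm, an imbalance would be visible. That helps a reader suspect bias, but it does not return the patients to the endpoint comparisons.

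A third is that the numbers are assumed and mostly modest. This is fair. Keeping everyone in example (a) would give Fisher power of only 0.9% to 3.4%. The largest figures, in (b) and the first part of (c), treat excluded patients as bleeders, and the 75% v 25% split in (c) has no source in the document. Operative blood loss is also listed as secondary only in section 18, not in section 12.

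Finally, the two nephrostomy-tube passages may describe different situations. They are then unclear rather than contradictory, but they still need reconciling because the exclusion depends on them.

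**Conclusion.** The concern holds, and the rule is wrong as written; it must be fixed. It is stated text, not a detail left to a separate analysis plan. Confidence is high: the incomplete-data trigger always acts after allocation and sustains the point alone. The bleeding trigger adds to it wherever bleeding begins during lithotripsy or the toss precedes access.

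The direction and size of the bias cannot be derived from the document. On the assumed inputs above, hidden differences in postoperative bleeding are 1.0 to 3.4 points, false ones are 0.8 to 5 points, and operative time shifts by no more than about 0.05 SD. With about 50 patients per arm and uncommon complications, a few deletions can change the safety result. The study's exploratory aim does not alter this, since it remains a randomised comparison tested at P<0.05.

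**What to change.** - **Section 10:** limit Exclusion 2 to conditions confirmed before allocation. Clarify the nephrostomy-tube criterion and reconcile it with the routine tube placement in section 11.c.c.
- **Section 16:** state when the coin is tossed relative to puncture, and align sections 11.a and 11.c.b with it.
- **Section 19:** make the main analysis all randomised patients in the group assigned. Keep patients with channel bleeding after allocation in every endpoint, including operative blood loss. Report channel bleeding by arm as an intraoperative event, without redefining the postoperative complication endpoint of section 12.
- **Missing data:** handle them endpoint by endpoint, so that intraoperative endpoints keep everyone operated on. Add a sensitivity analysis for missing postoperative endpoints.
- **Reduced set:** keep it only as a labelled sensitivity analysis.

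The cost is wording in sections 10, 16 and 19, the reconciliation with section 11, and slightly more analysis. No patients, procedures or endpoints are added. Complication figures may look slightly less favourable.

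### Seven endpoints are primary with no ranking or success rule, operation time is both primary and secondary, and the two secondary lists share no item

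*Protocol*

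**What the plan says.** **Protocol Section 12 (Outcome measures), primary.** The list begins "The primary clinical end point are operative time" and continues with six more: stone clearance, number of tracts, second operation, auxiliary procedure, injury to the renal pelvis mucosa, and postoperative complications. The last is a bundle, "including postoperative fever, bleeding, pain, and changes in renal function", to which two further complications are added.

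**Section 12, secondary.** "The secondary clinical end points were operation time, hospital stay, hospital cost".

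**Section 18 (Data collection).** The same seven reappear: "Data of the main end points included:operative time", and so on. The secondary list is a different one: "Secondary end points included:postoperative renal function changes, operative blood loss, postoperative bleeding rate, postoperative patient pain score", followed by a fifth item on inflammation.

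**Section 19 (Statistical analysis plan).** It names a test for each type of data and one threshold: P < 0.05 "was considered statistically significant". It gives no order of testing, division of alpha or rule for success.

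**Context.** Section 7 says "The purpose of this study is to explore the safety and clinical efficacy of this new surgical method" and Section 8 says "Prospective exploration studies were conducted on a 1:1 basis". Section 14 bases the 100 patients on clinic and surgical volume, so the sample size does not show which endpoint was meant to lead.

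**The concern.** A primary endpoint is the result by which a trial's question is answered. Here seven results hold that position. One of them, time in surgery, is also secondary within the same paragraph. It is also an outcome that Section 6 already says the technique improves. As the text stands, a favourable time result could be presented as primary and an unfavourable one as secondary, and both would be consistent with the protocol.

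The secondary endpoints are no firmer, because Sections 12 and 18 give two lists with nothing in common. With one unadjusted threshold and no success rule, the plan also leaves room to report any one of seven significant results as a positive primary finding. The chance of a false positive would then exceed the stated 5%.

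**Working it through.** **1. The lists side by side**

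| Status | Section 12 | Section 18 |
|---|---|---|
| Primary / main | 7 items | the same 7 items |
| Secondary | 3: time in surgery, length of stay, cost | 5: renal function, operative blood loss, bleeding rate, pain score, inflammation |

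- Overlap of the two secondary lists: 0 items (3 against 5).
- Items in both tiers within Section 12: one, time in surgery. No definition separates the primary wording from the secondary wording.
- A weaker overlap: bleeding, pain and renal function change are components of the primary complications endpoint and are also secondary in Section 18. Components may properly be reported separately, but the text does not say that this is intended.

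**2. Planned figure.** The only design figure is 100 patients at 1:1. It cannot be reproduced, because no effect size, SD, event rate or power is given.

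**3. Chance of at least one false positive if any one of the seven suffices**

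Inputs from the protocol: seven primaries, 0.05 per test, about 50 per arm (100 at 1:1). Assumed: two-sided tests, the correlations and the event rates.

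- Independent tests: 1 − 0.95^7 = 0.302.
- Equally correlated normal test statistics, by numerical integration: 0.230 at correlation 0.5 and 0.149 at 0.8.

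Five of the seven are rates (clearance, second operation, auxiliary procedure, mucosal injury, complications). Section 19 allows chi-square or Fisher tests for these. Fisher's test is conservative when events are few, so it was used for all five. Time in surgery and number of tracts were given t-tests; treating number of tracts as measurement data is an assumption. With independent endpoints the total is 1 − 0.95² × (1 − Fisher size)^5. The correlated columns come from a patient-level simulation of 40,000 runs.

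| Event rate | Exact Fisher size | Independent | Correlation 0.5 | Correlation 0.8 |
|---|---|---|---|---|
| 2% | 0.0004 | 0.099 | 0.094 | 0.080 |
| 5% | 0.0072 | 0.130 | 0.120 | 0.102 |
| 10% | 0.0179 | 0.175 | 0.158 | 0.132 |
| 20% | 0.0282 | 0.218 | 0.191 | 0.152 |

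Every entry in the last three columns is above 0.05.

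**4. Cost of the possible rules at 50 per arm (normal approximation)**

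The reference effect is the standardised difference detectable with 80% power at 0.05: (1.960 + 0.842) × √(2/50) = 0.560 SD. It is not a protocol figure.

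- *Holm, first step.* 0.05/7 = 0.0071, critical value 2.690. Power at 0.56 SD is Φ(0.56 × √(50/2) − 2.690) = Φ(0.110) = 0.544, against 0.800 at 0.05. The t-based values are 0.523 and 0.792.
- *Patients per arm for 80% power at 0.56 SD.* 2 × (z + 0.842)² / 0.56² gives 50.06 (so 51) at 0.05 and 79.5 (so 80) at 0.0071. With 50 per arm, the detectable difference at 0.0071 is (2.690 + 0.842) × √(2/50) = 0.706 SD.
- *All seven must succeed, each with 80% power (assumed).* Independent: 0.8^7 = 0.210. Correlation 0.5: 0.449. Correlation 0.8: 0.600.

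**The case against.** - **Multiplicity may be handled elsewhere.** A separate analysis plan may exist, and adjustment rules are often left to it. This has some force for the adjustment alone. It does not reach the contradictions, which lie inside the protocol; deciding which endpoints are primary is the protocol's own task. Section 19 is also headed as the analysis plan and fixes a single threshold.
- **The study is exploratory.** Sections 7 and 8 say so, no sentence makes one significant result a success, and the claims in Section 6 are background. This stands as a limit: the error-rate argument is conditional. Exploratory wording does not reconcile conflicting lists.
- **The double listing looks like a slip.** Time in surgery comes first among the primaries in both sections, and Section 18 does not list it as secondary. The balance of the text favours primary, but the duplicate still has to be removed before results are known.
- **The percentages rest on assumptions.** This is correct. The protocol gives no event rates or correlations, and it does not require Fisher's test for every rate. The figures show a range and are not a floor.
- **The component overlap is weak.** This is also correct: an overall complication rate and separate measures of pain or bleeding can coexist. The finding does not depend on it.
- **The Holm cost is a worst case.** It applies the strictest step; later steps are less demanding.

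**Conclusion.** The concern holds and must be fixed. The firm part needs no assumption: seven unranked primaries, one endpoint with two statuses in a single paragraph, and two secondary lists with no common item.

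The inflated error rate is a consequence, conditional on any one significant primary being reported as positive. It is then 30.2% for seven independent 5% tests, about 23% at correlation 0.5 and 15% at 0.8. With Fisher tests on the five rates and 50 per arm, it runs from about 8% (2% events, correlation 0.8) to 22% (20% events, independent). All exceed 5%. Confidence is high on the contradictions; the percentages are illustrative.

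**What to change.** Before results are known:

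1. **Name one primary endpoint in Section 12, tested two-sided at 0.05.** The choice is the investigators'. Operative time is a candidate because Section 6 claims the technique shortens it.
2. **Make all other endpoints secondary**, reported as differences with 95% confidence intervals.
3. **Give each endpoint one status.** Delete the second mention of operation time or define how it differs, and state whether bleeding, pain and renal function are reported as components, as separate endpoints, or both.
4. **Make Sections 12 and 18 carry the same lists**, and align Section 19.

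The cost is a change of wording in three sections, no extra patients, and fewer results that can be called primary.

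If all seven are to stay primary, Section 19 should state one of two rules:

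- **All must succeed.** No adjustment is needed. With 80% power for each, the chance of overall success is about 21% (independent), 45% (correlation 0.5) or 60% (correlation 0.8).
- **Holm across the seven.** At the first step, power for 0.56 SD falls from about 80% to about 54%. Restoring 80% needs about 80 rather than 51 per arm, or a true difference of about 0.71 SD.

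In either case the complications endpoint should be defined beforehand. The single primary is the cheapest option.
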